5.4.1.1 Permitted Concomitant Medications

5.5 Prevention of Pregnancy

Female patients of child-bearing potential must agree to use dual methods of contraception and have a negative serum pregnancy test at screening, and male patients must use an effective barrier method of contraception if sexually active with a female of child-bearing potential. Acceptable methods of contraception are condoms with contraceptive foam, oral, implantable or injectable contraceptives, contraceptive patch, intrauterine device, diaphragm with spermicidal gel, or a sexual partner who is surgically sterilized or post-menopausal. For both male and female patients, effective methods of contraception must be used throughout the study and for one month following the last dose.

5.6 Blood Products

During the administration of selinexor and ibrutinib, patients may receive red blood cell (RBC) or platelet transfusions, if clinically indicated, per institutional guidelines. These transfusions should be leukopore filtered and irradiated. Patients who require repeated transfusion support should be discussed with the principal investigator.

Patients may receive supportive care with G-CSF or GM-CSF in accordance with institutional guidelines prior to entry and throughout the study.

5.7 Radiation Treatment

If clinically indicated, palliative radiation therapy to non-target lesions is permitted but study drug should be held for 3-5 days before the start of palliative radiation therapy and 3-5 days after

palliative radiation therapy. Treatment with selinexor and ibrutinib shall not be discontinued solely due to palliative radiation. Additionally for patients responding to this treatment, if local radiation to a secondary cancer (prostate, skin, DCIS, etc.) is required, this can be considered after discussion with the PI.

5.8 Glucocorticoid Therapy

Glucocorticoids ≤ 10 mg oral prednisone (or equivalent) per day are permitted at baseline and during the study for non-malignant conditions (i.e., asthma, IBD, etc.) as needed.

As part of supportive care (e.g. for nausea or anorexia), oral or parenteral dexamethasone, up to 30 mg/week, may be given to patients, in consultation with the principal investigator. Doses of 2-4mg po qd, or 10mg with each dose of selinexor, can reduce fatigue, increase appetite, and improve energy in patients on study.

5.9 Anti-diarrheal Medications

Over-the-counter anti-diarrheal medications (such as loperamide or equivalent) may be used by the patient to control loose stools associated with the study medications. The medications should be used as directed by the package insert, pharmacist or treating physician.

5.10 General Medications

Medications to treat concomitant diseases like diabetes, hypertension, etc. are allowed.

5.11 Procedures

Refer to section 5.2.4 for guidelines on holding ibrutinib for procedures.

5.11.1.1 Prohibited Concomitant medications

Patients should minimize the use of products containing Acetaminophen. For combination painkillers containing acetaminophen it is recommended that single agent opiates or aspirin combinations (when clinically acceptable) be substituted.

5.12 Anticancer Therapy

Concurrent therapy with a systemic approved or investigative anticancer therapeutic, other than glucocorticoids as specified herein, is not allowed (this includes bone marrow transplantation for any reasons). Hormonal therapy is permitted.

5.13 Investigational Agents

Other investigational agents should not be used during the study.

5.14 Drugs undergoing Glutathione conjugation

The primary metabolism of selinexor *in vitro* appears to inactivation by glutathione conjugation. This process can be mediated in the absence of proteins, indicating that it is thermodynamically favorable. In vitro studies using human liver microsomes confirm in vivo findings that selinexor undergoes minimal CYP450 metabolism. Therefore, administration of selinexor with drugs which undergo substantial glutathione conjugation should be minimized or avoided. These drugs include acetaminophen (paracetamol). It should be noted that no studies selinexor in combination with acetaminophen have been performed to date and that these recommendations are empirical. There are no restrictions on the use of acetaminophen or acetaminophen-containing products in combination with selinexor, EXCEPT on days of selinexor dosing, when acetaminophen use must not exceed a total daily dose of 1 g.

5.15 Drugs that inhibit or induce CYP 3A4/5

Because there is a potential for interaction of ibrutinib with other concomitantly administered drugs through the cytochrome P450 system, the case report form must capture the concurrent use of all other drugs, over-the-counter medications, or alternative therapies. The Principal Investigator should be alerted if the patient is taking any agent known to affect or with the potential to affect selected CYP450 isoenzymes. Appendix B presents guidelines for identifying medications/substances that could potentially interact with ibrutinib.

5.16 Warfarin

Patients who must receive systemic anticoagulation with warfarin will be excluded secondary to severe bleeding when ibrutinib and warfarin have been used concurrently. Patients must be off warfarin for 30 days prior to enrollment. If individuals develop a DVT or other complications requiring anticoagulation, low molecular weight heparin or thrombin inhibitors may be used. Ibrutinib should be held for a minimum of 7 days to assure acceptable tolerance of this treatment. For patients with low risk atrial fibrillation, aspirin (325 mg/day) is recommended unless the patient is at high risk for thromboembolic complications.

5.17 Concomitant Treatments for Selinexor

Dexamethasone (12 mg) will be given as a concomitant medication with each dose of selinexor. For patients with partial intolerance to glucocorticoids, a minimum dose of 8 mg dexamethasone is permitted. Patients who are tolerating selinexor well may have the dose of dexamethasone decreased or eliminated at the discretion of the treating physician. Dexamethasone, like the other recommended prophylactic treatments in this study, is an approved drug. It will be provided in tablet form by prescription from the treating physician and obtained from the clinic pharmacy.

Required 5-HT₃ Antagonists: In order to minimize nausea, unless contraindicated, all patients must receive 5-HT₃ Antagonists (ondansetron 8 mg or equivalent) starting before the first dose of selinexor and continued bid – tid prn.

5.18 Supportive Care Guidelines for selinexor**TABLE: SUPPORTIVE CARE AND SELINEXOR DOSE ADJUSTMENT GUIDELINES FOR AES RELATED TO SELINEXOR^{A,B}**

Toxicity and Intensity	Supportive Care and Dose Adjustment Guidelines
Fatigue	
Grade 1	Maintain dose. Rule out other causes. If found to be anemic and symptomatic, consider transfusing even with hemoglobin >8 g/dL (anemia Grade <3). Patients with significant fatigue after several doses of selinexor may have an antitumor response. Consider an unscheduled assessment of tumor response as part of the patient's evaluation.
Grade 2 lasting ≤7 days	As per the NCCN guidelines, consider stimulants such as methylphenidate 5mg QD in the morning only.
Grade 2 lasting >7 days or Grade ≥3	Rule out other causes. If found to be anemic and symptomatic, consider transfusions for hemoglobin >8 g/dL (Grade <3); transfusions usually indicated for Hb <8 g/dL (Grade ≥3). Interrupt selinexor dosing until resolved to Grade 1 or baseline. For first occurrence, restart selinexor at current dose. For ≥ second occurrence, reduce selinexor by 1 dose level. Patients with significant fatigue after several doses of selinexor may have an antitumor response. Consider an unscheduled assessment of tumor response as part of the patient's evaluation. As per the NCCN guidelines, consider stimulants such as methylphenidate 5mg QD in the morning only.
Anorexia or Weight loss	
Grade 1 anorexia	Maintain dose. Rule out other causes. Consider nutritional consultation and use nutritional supplements (eg, Ensure [®] , Boost [®]). For persistent symptoms, start appetite stimulants, such as olanzapine (2.5 to 5 mg PO every morning) or megestrol acetate (400 mg QD), per NCCN guidelines.
Grade 1 weight loss Grade 2 anorexia	Initiate appetite stimulants, such as olanzapine (2.5 to 5 mg PO every morning) or megestrol acetate (400 mg QD), as per NCCN guidelines.
Grade 2 weight loss Grade 3 anorexia, or Grade 3 weight loss	Interrupt selinexor dosing until improved to Grade 1 or baseline and weight stabilizes. Reduce selinexor by 1 dose level. Rule out other causes. Consider nutritional consultation and use nutritional supplements (eg, Ensure [®] , Boost [®]) Start appetite stimulants as above,

Toxicity and Intensity	Supportive Care and Dose Adjustment Guidelines
Nausea, Acute	
Grade 1 or 2	
Maintain dose. Rule out other causes. Use standard additional anti-nausea medications to supplement the protocol-required 5-HT3 antagonists.
 
Use additional anti-nausea medications to supplement the protocol-required 5-HT3 antagonist(s). Olanzapine 2.5 to 5 mg PO every morning, per NCCN guidelines, can mitigate nausea and anorexia.

Grade 3	
Rule out other causes. Use additional anti-nausea medications to supplement the protocol-required 5-HT3 antagonist(s). Olanzapine 2.5 to 5 mg PO every morning, per NCCN guidelines, can mitigate nausea and anorexia.
 
Interrupt selinexor dosing until resolved to Grade ≤ 2 or baseline and reduce selinexor by 1 dose level.
 
Patients with significant nausea/vomiting after several doses of selinexor may have an antitumor response. Consider an unscheduled assessment of tumor response as part of the patient's evaluation.

Hyponatremia	
Grade 1 (sodium levels < Normal to 130 mmol/L)	
Maintain dose. Rule out other causes including drug (eg, diuretic) effects. Be certain that reported sodium level is corrected for concurrent hyperglycemia (serum glucose >150 mg/dL).
 
Treat hyponatremia per institutional guidelines including dietary review. Provide supplemental oral and/or intravenous fluids if dehydration is present. Consider addition of salt tablets to patient's diet.

Grade 3 with sodium levels <130-120 mmol/L without symptoms	
Rule out other causes including drug (eg, diuretic) effects. Be certain that reported sodium level is corrected for concurrent hyperglycemia (serum glucose >150 mg/dL).
 
If (corrected) sodium is Grade ≤ 3 and continues to be asymptomatic, then patient may continue current dosing without interruption provided that IV saline and/or salt tablets are provided and patient is followed closely.
 
If Grade 3 is persistent or worsens or does not respond to treatment, interrupt selinexor dosing until resolved to Grade 1 or baseline and reduce selinexor by 1 dose level.

Grade 3 with sodium levels <130-120 mmol/L with symptoms or Grade 4 (<120 mmol/L)	
Rule out other causes including drug (eg, diuretic) effects. Be certain that reported sodium level is corrected for concurrent hyperglycemia (serum glucose > 150 mg/dL).
 
Interrupt selinexor dosing until resolved to Grade 1 or baseline and without symptoms. Reduce selinexor by 1 dose level.

Diarrhea	
Grade 1	
Maintain dose. Rule out other causes including drug effects. Treat per institutional guidelines with anti-diarrheals, such as loperamide.

Grade 2	
Rule out other causes including drug effects. Treat per institutional guidelines with anti-diarrheals. Interrupt selinexor dosing until resolved to Grade 1 or baseline.
 
For first occurrence, restart selinexor at current dose.
 
For \geq second occurrence, reduce selinexor by 1 dose level.

Grade 3 or 4	
Interrupt selinexor dosing until resolved to Grade 1 or baseline and patient is clinically stable. Reduce selinexor dose by 1 dose level.

Thrombocytopenia	
Grade 1 or 2	
Maintain dose. Rule out other causes including drug effects.

Toxicity and Intensity	Supportive Care and Dose Adjustment Guidelines
Grade 3 without bleeding	
Rule out other causes including drug effects.
 
For first occurrence: skip 1 dose and reduce selinexor by 1 dose level.
 
If recurrent, unless contraindicated, start treatment with moderate to high doses of thrombopoietin stimulating agents such as romiplostim 5 to 10 µg/kg SC weekly (preferred) or eltrombopag 100 to 150 mg QD.
 
In cases where there is significant disease involvement in the bone marrow or pre-existing compromised marrow function (eg, due to prior marrow-toxic therapy), or if there is baseline thrombocytopenia Grade 2-4 at baseline, the Investigator in consultation with the Medical Monitor may decide to continue selinexor dosing without dose reductions and/or interruptions as specified above, provided that platelet counts and bleeding symptoms/signs are closely monitored. Thrombopoietin stimulating agents are recommended.

Grade 4 without bleeding	
Rule out other causes including drug effects.
 
Interrupt selinexor until patient recovers to Grade 2 or baseline. Selinexor dosing may be reduced by 1 dose level (it is recommended to have only 1 dose modification per cycle).
 
If recurrent, unless contraindicated, start treatment with moderate to high doses of thrombopoietin stimulating agents as above.
 
In cases where there is significant disease involvement in the bone marrow or pre-existing compromised marrow function (eg, due to prior marrow-toxic therapy), the Investigator in consultation with the Medical Monitor may decide to continue selinexor dosing without dose reductions and/or interruptions as specified above, provided that platelet counts and bleeding symptoms/signs are closely monitored.

Grade ≥ 3 with bleeding	
Interrupt selinexor dosing and check platelet counts weekly until the bleeding has stopped, patient is clinically stable and the platelets have recovered to Grade 2 or baseline. When resuming selinexor, reduce by 1 dose level.
 
If recurrent, unless contraindicated, start treatment with moderate to high doses of thrombopoietin stimulating agents as above.

Neutropenia	
Grade 3 or 4 neutropenia (afebrile) OR Febrile neutropenia	
Institute colony stimulating factors and prophylactic antibiotics as clinically indicated per institutional guidelines.
 
Interrupt selinexor and check neutrophils at least weekly until recovers to Grade 2 or baseline and without fever (if febrile) and the patient is clinically stable. Reinitiate selinexor therapy and colony stimulating factors per institutional guidelines.
 
If recurrent, continue colony stimulating factors, interrupt selinexor until neutrophil counts improve to Grade ≤ 2 or baseline levels, and reduce dose of selinexor 1 dose level.

Anemia	
Treat per institutional guidelines including blood transfusions and/or erythropoietins. Consider transfusing for symptoms with hemoglobin >8 g/dL (Grade <3) or for any Grade 3 (hemoglobin <8 g/dL). If possible, maintain selinexor dose as long as patient is clinically stable, but if a dose reduction or interruption is desired, consult with the Medical Monitor.	

Toxicity and Intensity	Supportive Care and Dose Adjustment Guidelines
Tumor lysis syndrome	
If TLS risk factors are identified, provide prophylactic IV hydration and regular monitoring of hydration (especially when increasing the dose of selinexor), renal function, urine output, and clinical laboratory measures of interest for TLS (eg, phosphorus, potassium, calcium, LDH, uric acid). Consider administration of hypouricemic agents to reduce the risk of TLS. Hold selinexor in patient with hyperkalemia (≥ 7.0 mmol/L) and/or symptoms of hyperkalemia, an increase in uric acid, or other changes in biochemical blood parameters suggestive of TLS. Start IV hydration, and consider hypouricemic agent until levels return to normal. Selinexor can be reintroduced at the normal or reduced dose.	
Other selinexor-related adverse events	
Grade 1 or 2	Rule out other causes. Maintain dose. Start treatment and/or standard supportive care per institutional guidelines.
Grade 3 or 4	Rule out other causes. Interrupt selinexor until recovers to Grade 2 or baseline and reduce selinexor by 1 dose level. Isolated values of Grade ≥ 3 alkaline phosphatase do NOT require dose interruption. Determination of liver versus bone etiology should be made, and evaluation of gamma-glutamyl transferase, 5'-nucleotidase, or other liver enzymes should be performed.

- ^AFOR ALL GRADE ≥ 3 HEMATOLOGIC OR NON-HEMATOLOGIC AES THAT ARE NOT SELINEXOR RELATED, AFTER CONSULTATION WITH THE MEDICAL MONITOR AND AT THE DISCRETION OF THE INVESTIGATOR, SELINEXOR DOSING MAY BE MAINTAINED.**
- ^BFOR ALL SELINEXOR-RELATED AE'S, IF THE BELOW PRESCRIBED DOSE REDUCTIONS/INTERRUPTIONS RESULT IN A STABILIZATION OF ≥ 4 WEEKS, A RE-ESCALATION MAY BE CONSIDERED AFTER APPROVAL FROM THE MEDICAL MONITOR.**
- ALL DOSE MODIFICATIONS SHOULD BE BASED ON THE WORST PRECEDING TOXICITY.**
- NOTE: WHEN TOXICITIES DUE TO SELINEXOR HAVE RETURNED TO BASELINE LEVELS OR THE PATIENT HAS STABILIZED, THE DOSE OF SELINEXOR MAY BE RE-ESCALATED IN CONSULTATION WITH THE MEDICAL MONITOR.**

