6.1 Dose adjustment guidelines for hematologic ibrutinib or selinexor-related toxicities

Toxicities that are clearly not related to ibrutinib or selinexor will not require a dosing modification. Similarly, toxicities that are clearly attributable to an individual drug will only require modification of that drug, with modifications following the tables below.

Event Name	Neutropenia, Anemia, or Thrombocytopenia For Patients with Baseline Absolute Neutrophil Count $\geq 1000/\text{mm}^3$; Hemoglobin $\geq 11\text{g/dL}$; or Platelets $\geq 100,000/\text{mm}^3$	
Grade of Event	Management/Next Dose Ibrutinib*	Management/Next Dose of Selinexor*
< Grade 3	No change in dose	No change in dose
\geq Grade 3	Hold until neutrophils, hemoglobin, or platelets have returned to < Grade 3. • 1 st occurrence: No change in dose • 2 nd occurrence: Cohort 1 and 3 = No change in dose; Cohort 2 = Decrease ibrutinib to next lowest dose level • 3 rd occurrence: Decrease ibrutinib to next lowest dose level • 4 th occurrence: Patient comes off study	Hold until neutrophils, hemoglobin, or platelets have returned to < Grade 3. • 1 st occurrence: No change in dose • 2 nd occurrence: Decrease selinexor to next lowest dose. • 3 rd occurrence: No change in dose • 4 th occurrence: Patient comes off study
*Dose reductions < ibrutinib 140mg daily or selinexor 20 mg weekly are not permitted. Recommendations: - Full supportive care, growth factors, and transfusions should be given as medically indicated. - If the patient tolerates a reduced dose for two cycles, patient may be dose escalated to the dose they received prior to the reduction after authorization from Principal Investigator.		

Event Name	Neutropenia, Anemia, or Thrombocytopenia For Patients with Baseline Absolute Neutrophil Count $\leq 1000/\text{mm}^3$; Hemoglobin $\leq 11\text{g/dL}$; or Platelets $\leq 100,000/\text{mm}^3$
------------	---

Grade of AE	Management/Next Dose Ibrutinib*	Management/Next Dose of Selinexor*
<Grade 3	No change in dose	No change in dose

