		resolved to Grade ≤ 2 , then reinitiate selinexor at one dose level below. If patient is stable and diarrhea resolves (Grade 0 or baseline with or without anti-diarrheals) for 4 weeks, then the patient's dose may be re-escalated.

Recommendations:
 
-Full supportive care and antidiarrheal agents. See Section 4.4.
		

Event Name	Fatigue	
Grade of Event	Management/Next Dose Ibrutinib	Management/Next Dose of Selinexor
Grade 1	No change in dose	Ensure adequate caloric intake and assess volume status. Recommend high calorie and/or energy drinks and/or foods. Adjust other medications. Rule out other causes of fatigue such as adrenal insufficiency, hypothyroidism, etc.
Grade 2	No change in dose	Ensure adequate caloric and fluid intake and assess volume status. Add supportive care for fatigue, or reduce the dose of selinexor by one level. If patient's fatigue is Grade ≤ 1 for 4 weeks, then the dose of selinexor may be increased back to the previous dose level.
Grade 3	No change in dose	Ensure adequate caloric and fluid intake and assess volume status. Interrupt selinexor dosing until resolved to Grade ≤ 2 , reduce dose of selinexor by 1 level. If patient's fatigue is Grade ≤ 1 for 4 weeks, then the dose of selinexor may be increased back to the previous dose level.

Recommendations:
 
- Optimize supportive care including caloric and fluid intake. Add glucocorticoids when not contra-indicated. See Section 4.4.
		

Event Name	Rash - Maculopapular	
Grade of Event	Management/Next Dose Ibrutinib*	Management/Next Dose of Selinexor*
\leq Grade 1	No change in dose	No change in dose
Grade 2	Hold until \leq Grade 1. Resume same dose.	No change in dose

Grade 3	Hold until toxicity \leq Grade 1. • 1 st occurrence: Decrease ibrutinib to next lowest dose level. • 2 nd occurrence: Decrease ibrutinib to next lowest dose level.	Hold until toxicity \leq Grade 1 or baseline. • 1 st occurrence: No change in dose. • 2 nd occurrence: Decrease selinexor to next lowest dose level.
*Dose reductions < ibrutinib 140 mg daily or selinexor 20 mg weekly are not permitted. Recommendations: - Review medication list and discontinue any medications that commonly cause rash if possible. -Consider skin biopsy.		

Event Name	Thrombosis/Thromboembolic Event	
Grade of Event	Management/Next Dose Ibrutinib	Management/Next Dose of Selinexor
\leq Grade 1	No change in dose	No change in dose

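### Section 5.18 and Sections 6.1/6.2 give contradictory selinexor instructions for three severe toxicities, and no sentence says which section governs

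*Combined protocol and SAP*

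**What the plan says.** The table in Section 5.18 combines supportive care with selinexor dose adjustment; its title names both. Sections 6.1 and 6.2 are dose-adjustment tables for toxicities of either drug.

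- **Thrombocytopenia, Grade 3, no bleeding, first event.** Section 5.18: "For first occurrence: skip 1 dose and reduce selinexor by 1 dose level". For patients with marrow involvement, compromised marrow or low baseline platelets, the investigator and Medical Monitor "may decide to continue selinexor dosing without dose reductions and/or interruptions as specified above". Section 6.1, for baseline platelets of at least 100,000: "Hold until neutrophils, hemoglobin, or platelets have returned to < Grade 3", and the entry for the first event reads "occurrence: No change in dose". A reduction comes only at the second event.
- **Fatigue, Grade 3, first event.** Section 5.18 interrupts until Grade 1 or baseline, then: "For first occurrence, restart selinexor at current dose". Section 6.2 interrupts until Grade 2 or lower and then says "reduce dose of selinexor by 1 level".
- **Grade 4 non-hematologic events.** Section 5.18, for Grade 3 or 4 diarrhea: "Interrupt selinexor dosing until resolved to Grade 1 or baseline and patient is clinically stable. Reduce selinexor dose by 1 dose level". Its row for other selinexor-related Grade 3 or 4 events: "Interrupt selinexor until recovers to Grade 2 or baseline and reduce selinexor by 1 dose level". Section 6.2 stops the responsible drug for good after any Grade 4 toxicity at least possibly due to study treatment. Transaminase and electrolyte events must last 7 days or more for this to apply.

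**The concern.** A selinexor-related event falls under both sections. Section 5.18 covers adverse events related to selinexor, and the opening of Section 6.1 sends toxicities attributable to one drug to its own tables. Two patients with the same event could therefore be handled differently in a multi-center trial, each by a rule printed in the protocol. In the third case one rule re-exposes a patient whom the other takes off the drug permanently.

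What is at stake is dosing safety after severe toxicity. A lesser consequence is for the descriptive tolerability summary in Section 13.8.1, where counts of dose reductions and reasons for stopping would mix two policies. That summary is itself optional.

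**Working it through.** There is no planned statistical figure to reproduce. The check is a comparison of the rules, then the dose each one gives.

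**Inputs.** Assigned dose 40 mg weekly; one level down is 20 mg weekly (Section 5.2.3). Dosing is on days 1, 8 and 15 of a 28-day cycle, so 3 × 40 = 120 mg per cycle in full and 3 × 20 = 60 mg one level down.

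| Event | Section 5.18 | Section 6 | Restart dose, 5.18 vs 6 |
|---|---|---|---|
| First Grade 3 thrombocytopenia, no bleeding, baseline platelets ≥100,000, waiver not used | omit one dose, down one level | hold to below Grade 3, same dose | 20 vs 40 mg |
| First Grade 3 fatigue | hold to Grade 1 or baseline, same dose | hold to Grade ≤2, down one level | 40 vs 20 mg |
| Attributable Grade 4 non-hematologic event, e.g. diarrhea, cycle 2 on | hold, down one level | stop permanently | 20 mg vs none |

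Each difference is 20 mg per week: 20/40 = 50% of the assigned dose, or 120 − 60 = 60 mg per full cycle (60 − 0 = 60 mg in the third row). Section 5.18 gives the lower dose in the first row and the higher in the other two, so neither section is uniformly the cautious one.

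**When each row can arise.** Section 6 removes patients with a cycle 1 DLT, and Section 5.3 counts Grade 4 non-hematologic toxicity as a DLT, so the third row matters from cycle 2. Grade 3 thrombocytopenia without bleeding and Grade 3 fatigue lasting under 7 days do not in themselves meet the DLT criteria. The first two rows can therefore arise in cycle 1 as well, unless a delay exceeds 28 days or the event is classed as a DLT by the discretion in Section 5.3.

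**How long the gap lasts.** The 50% is the gap at restart. A footnote to 5.18 allows re-escalation after at least 4 weeks of stabilization with Medical Monitor approval. Section 6.1 allows it after two tolerated cycles (2 × 28 = 56 days) with principal investigator authorization. The 6.2 fatigue row allows it after 4 weeks at Grade 1 or lower. The first two gaps may thus last one to two cycles, or longer if re-escalation is not used. Permanent discontinuation in the third row has no such route back.

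**Search for a ranking rule.**
- Sections 6 and 6.1 direct modifications to the material that follows them, which implies that Section 6 governs. Neither mentions 5.18.
- Sections 5.2 and 5.3, as printed, send the reader to Section 5 for dose modifications. That is the section containing 5.18.
- The lowest-dose rule in Sections 6 and 6.2 applies when a patient has several adverse events, not when two rules address one event.
- Section 6.7 requires consultation with the principal investigator but supplies no rule to apply.

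**The case against.** The best reply is that Section 6 plainly governs. Its wording points that way, and the references to Section 5 look like leftovers from old numbering: Section 8.1.5 likewise sends thrombocytopenia dose adjustments to Section 5.1, which is now the overview. Every modification also goes through the principal investigator, and sites hold monthly calls. Much of this stands, and it makes divergent handling less likely. It does not remove the conflict. The sentence in Section 5.2 just before the reference to Section 5 points to Section 7 for adverse events, which is correct under current numbering, so a site has reason to take both literally.

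A reader might infer more than the documents support:

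- **That dose finding is compromised.** The DLT definition in Section 5.3 and the dose-assignment rule in Section 13.7 do not depend on which table is followed after an event.
- **That patients stay on half the dose.** Re-escalation is permitted in the first two rows.
- **That the tables conflict throughout.** Rash has its own table in 6.2, which naturally takes precedence over the residual row in 5.18. Asymptomatic hyponatremia largely reconciles through the Section 6.5 exception for reversible electrolyte abnormalities. For febrile neutropenia 5.18 names no restart dose, so a conflict is inference only. Running out of reduction steps at 20 mg weekly is a separate matter within Section 6.

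**Conclusion.** The inconsistency is real and should be fixed. It is confined to three events: first Grade 3 thrombocytopenia without bleeding, first Grade 3 fatigue, and attributable Grade 4 non-hematologic toxicity after cycle 1. The third is the most serious because it decides between re-exposure and stopping.

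The dose figures assume a patient on 40 mg weekly and, for thrombocytopenia, a baseline platelet count of at least 100,000 with the Medical Monitor waiver not used. The third row excludes transaminase and electrolyte events shorter than 7 days. How many patients would be affected cannot be estimated, because the documents give no rates for these events on the combination.

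**What to change.** State in Section 6 that it is the sole source of selinexor dose modifications. Remove dose instructions from 5.18, and change the references to Section 5 in Sections 5.2 and 5.3 to Section 6.

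Extend the lowest-dose rule to conflicting instructions for a single event, and write the resulting values into Section 6:

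- **Grade 3 thrombocytopenia without bleeding:** hold to below Grade 3, omitting at least one dose, and resume one level lower.
- **Grade 3 fatigue:** hold to Grade 2 or lower, as 6.2 now says, and resume one level lower.
- **Attributable Grade 4 non-hematologic toxicity:** permanent discontinuation, as 6.2 now says.

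Naming the values matters. Declaring that Section 6 governs, without more, would leave thrombocytopenia at 40 mg, while a lowest-dose rule gives 20 mg. Keep the 7-day qualifier, the Section 6.5 electrolyte exception, the Medical Monitor waiver (moved to 6.1) and the existing re-escalation provisions. A 5.18 hold with no counterpart in Section 6, such as the one for tumor lysis, should be moved rather than deleted.

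The cost is one short amendment with notice to sites; no patients, procedures or data fields are added. If Section 6 is already being followed, only the thrombocytopenia row changes: up to 60 mg less selinexor per cycle after a first event, until re-escalation.
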